#### 12.3.6 Univariate CoR: Nonparametric threshold regression modeling

The van der Laan et al. (2021) extension of the nonparametric CoR threshold estimation method of Donovan et al. (2019) is applied to each of the five nonbaseline subtracted Day 57 antibody markers, using the version that defines the binary outcome Y of interest as Y = 1 if a COVID endpoint occurred during the blinded period of follow-up and Y = 0 otherwise. The analyses adjust for the same baseline factors X as used in the Cox model CoR analyses.

The extension adjusts for baseline covariates by estimating the conditional mean function  $E[Y|S \ge s, X, A = 1]$  using discrete-SuperLearner and then

empirically averaging over the baseline covariates X to estimate the marginal risk  $risk_1^Y(S \ge s) = E_X[P(Y = 1 | S \ge s, X, A = 1)]$  for each threshold s of the the antibody marker in a specified discrete set. We do not perform pooled regression across the thresholds s, which ensures we are totally nonparametric in estimating the threshold dependence of  $risk_1^Y(S \ge s)$  on s. The Super-Learner library includes a range of increasingly flexible parametric learners including logistic regression (glm), bayesian logistic regression (bayesglm), and L1-penalized logistic regression (glmnet). (Two of each learner is included in the library, one with only main-term variables and another with main-term and interaction variables.) An advantage of the nonparametric CoR threshold method compared to Cox modeling that specifies a log linear hazard ratio with the marker is that it can potentially detect a threshold of very low risk. The method is implemented with and without the monotonicity constraint that  $risk_1^Y(S \ge s)$  is monotone non-increasing in s, where the results assuming monotonicity are reported unless there is evidence for violation of this assumption.

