#### 15.1 CoP: Controlled Vaccine Efficacy

We first describe the controlled vaccine efficacy curve defined as

$$CVE(s) = 1 - \frac{P(Y(1,s) = 1)}{P(Y(0) = 1)}$$

The value CVE(s) takes represents the relative decrease in endpoint frequency achieved by administering vaccine and setting Day 57 immunologic marker level to s compared to the placebo control intervention. Under our approach, the value of CVE(s) is assumed to be monotone non-decreasing in s; in other words, vaccine efficacy can only potentially be improved by setting greater marker levels. The extent to which the marker plays a role in determining vaccine efficacy can be determined by the degree of flatness of the graph of CVE(s) versus s.

In addition, because the primary study cohort for correlates analysis is naive to SARS-CoV-2, each of the Day 57 markers S has no variability in the placebo arm [all values are 'negative,' below the assay lower limit of detection (LLOD)]. Therefore, advantageously in this setting CVE(s) has a special connection to the mediation literature, where CVE(s = LLOD) is the natural direct effect, and vaccine efficacy is 100% mediated through S if and only if CVE(s = LLOD) = 0. Thus inference on CVE(s = LLOD) evaluates full mediation.

Since P(Y(0) = 1) = P(Y = 1 | A = 0) in view of vaccine versus placebo randomization, the controlled vaccine efficacy CVE(s) at level s can be identified using the fact that

$$P(Y(1,s) = 1) = E[P(Y = 1 | S = s, A = 1, X)]$$

whenever Y(1,s) and S are independent given A = 1 and a vector X of covariates, and P(S = s | A = 1, X) > 0 almost surely. In other words, identification of the controlled vaccine efficacy requires that a rich enough

set of covariates be available so that deconfounding of the relationship between endpoint Y and marker S is possible in the subpopulation of vaccine recipients, and that marker level S = s may occur within each subpopulation defined by values of the covariates X (positivity).

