For each s, the identified parameter corresponding to CVE(s) is an irregular parameter within nonparametric models, making its estimation at root-n rate impossible; this significantly complicates estimation and inference on CVE(s). Fortunately, the monotonicity of  $s \mapsto \text{CVE}(s)$  provides an opportunity to circumvent these difficulties. Similarly to Westling et al. (2020a)'s approach for the causal dose-response function, we will use the general methodological template proposed in Westling and Carone (2020) to derive (i) a nonparametric Grenander-type estimator of CVE(s) and (ii) a plug-in confidence interval for CVE(s) based on an asymptotic Chernoff limit. This estimator will require, as an intermediate step, estimation of several nuisance functions, including the outcome regression P(Y = 1 | S = s, A = 1, X = x) and the propensity score P(S = s | X = x, A = 1). These nuisance functions will be estimated using the Superlearner ensembling algorithm with a rich library including both parametric regression methods as well as flexible machine learning tools.

The monotonicity-based procedure we will develop facilitates statistical inference for CVE(s) for each s separately, where point estimates and 95% confidence intervals for CVE(s) will be presented. However, it is also of interest to investigate whether the Day 57 marker plays a role in determining vaccine efficacy. To do so, we will formally test the null hypothesis

$$H_0$$
: CVE $(s)$  is constant in  $s$ 

against various alternatives. We will first adapt the approach of Westling (2020) to devise a nonparametric omnibus test of this null hypothesis. We will also construct a nonparametric directional test of this hypothesis tailored to alternatives under which CVE(s) is monotone in s, along the lines of Hall and Heckman (2000), for example. Leveraging the known monotonicity of the controlled vaccine efficacy will provide greater power than omnibus tests.

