Only this Superlearner analysis uses data from multiple assays and multiple readouts as input features; the other analyses consider one Day 57 biomarker at a time. The positivity

assumptions are as follows. Controlled VE: P(S = s | A = 1, X) > 0 almost surely. Stochastic Interventional VE:  $s_i \in S \implies s_i + \delta \in S | A = 1, X = x$  for all  $x \in \mathcal{X}$  and i = 1, ..., n. Mediators of VE: P(S = s | A = 1, X) > 0 almost surely and

P(S = s | A = 0, X = x) > implies P(S = s | A = 1, X = x) > 0. The quantitative analysis will require that the largest value S observed in the placebo is larger than the smallest value of S observed in the vaccine recipients. This assumption would naturally be satisified for the tertiles analysis. For quantitative S, the assumption is weaker for the Stochastic Interventional VE analysis, such that it is possible that only this analysis of the three will be done.
Some of the analyses include parametric assumptions for characterizing associations (Cox model and threshold analyses, Cox model versions of Controlled VE analyses) and others are nonparametric or approximately so (all other analyses). If parametric and nonparametric analyses of the same type (e.g., Cox model vs. nonparametric CoR analysis of the same association parameter; Controlled VE Cox model vs. nonparametric monotone dose-response) suggest contradictory results, then the interpretation from the nonparametric analysis will be prioritized, given it is more robust and less likely to be an incorrect result. The diagnostic testing of the parametric assumptions will aid this interpretation. As noted above, if the nonparametric analysis suggesting a contradictory result requires a positivity assumption, then its results will only be prioritized if diagnostics support feasibility of the positivity assumption.

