### 16.2 Multiple Hypothesis Testing Adjustment for CoP Analysis

For the univariable CoP analyses of the prioritized set of Day 57 antibody markers among the five specified marker variables, the analysis plan seeks evidence of a CoP through four different causal effect approaches. Because of this looking for evidence through different lenses, for CoP analysis we do not focus on family-wise error rate adjustment, because FWER-adjustment aims to control the risk of making even a single false rejection. Rather, in an effort to build a body of consistent evidence and to ensure that a large fraction of that evidence is reliable, for CoP analysis we focus on false discovery rate correction. To do this, we use the same permutation-based method (Westfall et al., 1993) that is used for CoR analysis. The multiplicity adjustment is performed across the Day 57 markers and across the set of CoP methods that are applied, in a single suite of hypothesis tests with calculation of q-values. As a guideline for interpreting CoP findings (but not meant to be a rigid gateway), markers with unadjusted p-value  $\leq 0.05$  and q-value  $\leq 0.10$  are flagged as having statistical evidence for being a CoP.

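### Section 16 ranks the monotone-constrained controlled VE fit above the Cox fit as more robust, but that fit cannot show VE falling with the marker, so it should not win a conflict about direction

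*Combined protocol and SAP*

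**What the plan says.** Section 15.1 defines the controlled vaccine efficacy curve CVE(s). Under the planned approach, "the value of CVE(s) is assumed to be monotone non-decreasing in s". The point estimate is a Grenander-type estimator and its interval uses a Chernoff limit; both depend on that shape. The section later treats the shape as established: "Leveraging the known monotonicity of the controlled vaccine efficacy will provide greater power than omnibus tests". It also plans "to devise a nonparametric omnibus test of this null hypothesis", where the null is that CVE(s) is constant. It gives no test of whether CVE(s) is non-decreasing.

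Section 16 sets the rule for contradictory results and lists "Controlled VE Cox model vs. nonparametric monotone dose-response" as an example of a pair it covers. On conflict, "then the interpretation from the nonparametric analysis will be prioritized, given it is more robust and less likely to be an incorrect result". A nonparametric analysis that needs positivity gets priority only if diagnostics support positivity. The other diagnostics mentioned concern the parametric model. Table 10 likewise lists only positivity as a contingency for controlled VE.

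Section 12.3.6 handles its own monotonicity assumption differently. The threshold curve is fitted with and without the constraint, "where the results assuming monotonicity are reported unless there is evidence for violation of this assumption".

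Section 16.2 pools p-values across markers and CoP methods. Markers with an unadjusted p-value of at most 0.05 and a q-value of at most 0.10 "are flagged as having statistical evidence for being a CoP". No direction is required.

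**The concern.** A fit that is non-decreasing by construction carries no information against a falling curve. When the Cox model shows risk rising with the marker and the constrained fit does not, the disagreement is produced by the constraint. The stated reason for preferring the nonparametric fit, that it is less likely to be wrong, does not hold for that disagreement.

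An inverse estimate is not far-fetched. The definition of the sample-size ratio in Section 12.5.2 has explicit cases for markers with a positive association with risk. Section 16.1 recognises that some early cases may have been infected before Day 57 and carry infection-induced antibody. Section 15.1.1 accepts that adequate adjustment for confounding can never be certain. In each setting the inverse Cox estimate is a useful warning, and the rule as written tells the interpreter to give it second place.

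**Working it through.** The plan states no figure on this point, so there is none to reproduce. The check has two parts.

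**1. What the constraint does.** Non-decreasing CVE(s) means non-increasing risk in s. If observed risk increases throughout the marker range, the closest non-increasing curve is a constant equal to the average risk. The constrained CVE curve is then flat at overall VE, however steep the true fall. More data make this flatness more certain.

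**2. Size.** Inputs from the SAP:
- 50 vaccine cases, the minimum for controlled VE (Table 4);
- a baseline-negative vaccine subcohort of 6 × 150 = 900 (Table 5);
- placebo risk 0.10 and VE 0.90 (simulation defaults, Section 24.3.1), so mean vaccine-arm risk is 0.10 × (1 − 0.90) = 0.01.

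Assumptions: a standard normal marker, hazard ratios of 1.5 and 2.0 per SD in the inverse direction, no covariates. A weighted logistic fit stands in for the Cox model, and weighted isotonic regression for the covariate-adjusted Grenander-type estimator. There were 600 runs per row.

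True curve: CVE(z) = 1 − 0.01·exp(βz − β²/2)/0.10, at z = ±1.036 (15th and 85th percentiles). For a hazard ratio of 1.5, β = 0.405 and β²/2 = 0.082:
- 15th: exp(−0.420 − 0.082) = 0.605, so CVE = 0.939
- 85th: exp(0.420 − 0.082) = 1.402, so CVE = 0.860

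| Cases | HR per SD | True CVE, 15th to 85th | Log-linear fit (mean) | Inverse slope significant | Monotone fit (mean) | Monotone fit exactly flat | Monotone fit falling |
|---|---|---|---|---|---|---|---|
| 50 | 1.0 | 0.900 to 0.900 | 0.899 to 0.900 | 2% | 0.883 to 0.916 | 18% | 0% |
| 50 | 1.5 | 0.939 to 0.860 | 0.939 to 0.860 | 79% | 0.899 to 0.900 | 90% | 0% |
| 50 | 2.0 | 0.962 to 0.839 | 0.962 to 0.838 | 100% | 0.900 to 0.900 | 100% | 0% |
| 200 | 1.5 | 0.939 to 0.860 | 0.940 to 0.860 | 100% | 0.900 to 0.900 | 100% | 0% |

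Percentages are rounded. At 50 cases and a hazard ratio of 1.5, the 10% of runs that were not flat rose.

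**Second setting.** With VE 80% and an arm of 13,000 (both assumed), again with 50 cases and 900 controls, the true fall at a hazard ratio of 1.5 is 88% to 72%. Results for the monotone fit:
- It never fell.
- Between the 15th and 85th percentiles it rose in 11% of runs at a hazard ratio of 1.5, by more than 5 points in 1.4%. At 1.3 it rose in 31%, by more than 5 points in 9%.
- Between the 5th and 95th percentiles it rose in 27% at 1.5 and 55% at 1.3. When the true curve was flat it rose in 94%.

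So a rising point estimate is ordinary noise of isotonic fitting, and it is less common when the truth is inverse than when it is flat.

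**The case against.** **Nothing is suppressed.** The rule concerns interpretation. Section 15.1.1 still plots the Cox marginalized and controlled risk curves with intervals. The Cox hazard ratios, the unconstrained threshold fit, the GAM and hinge fits, VE(1) − VE(0) and stochastic VE can all show an inverse pattern. This stands. A reader might infer that the inverse evidence disappears from the report; the documents do not support that.

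**A flat curve is the right answer for CoP status.** Section 15.1.1 requires risk to fall strictly somewhere before a marker counts as a controlled risk CoP. This also stands. A reader might infer that inverse markers will be declared protective. The simulations show mostly flat curves, and intervals accompany the point estimates.

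**Monotonicity is plausible for the causal curve, and an inverse Cox curve may itself be confounded.** Agreed, and this is why the Cox curve should not simply replace the constrained one. But if the causal curve is monotone, a clear inverse estimate suggests that the no-unmeasured-confounding assumption has failed. The constrained fit rests on the same assumption, so it deserves no priority either.

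**An unconstrained CVE(s) is not a simple extra fit.** Section 15.1 explains that CVE(s) cannot be estimated at root-n rate nonparametrically and that monotonicity is what makes inference feasible. Section 12.3.6 targets a different parameter, risk given S ≥ s. This stands, so its rule cannot be copied across unchanged. Its unconstrained fit is still informative on direction: if risk increases in s, so does risk given S ≥ s.

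**The 16.2 flag is only a guideline.** Section 16.2 says so, and Section 16.1 puts magnitude and direction above significance. No calculation here estimates how often an omnibus test would flag an inverse marker, so that part is a gap in wording without a measured size.

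**Conclusion.** The point holds for conflicts about direction. Section 16 gives priority, on grounds of robustness, to a fit that cannot show one of the two directions, and positivity is the only condition. Section 15.1 supplies no monotonicity check to make up for this.

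For a marker whose estimated risk rises with its level, the prioritized interpretation will usually be a flat CVE curve. At 50 cases and a hazard ratio of 1.5 per SD, it was flat in 90% of runs and falling in none, while the log-linear fit detected the inverse slope in 79%. Larger case counts do not cure it. The exact percentages depend on the assumed VE, hazard ratios, absence of covariates and simplified estimators. The absence of any fall follows from the constraint and depends on none of these.

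The consequence is that evidence of an inverse association is given second place, along with the warning it carries about confounding, early infection or assay failure. It is not a routine false declaration of a CoP, nor the loss of the Cox results. The change is worth making before the SAP is final, mainly because it costs so little.

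**What to change.** - **Section 16:** add monotonicity beside positivity as a condition. The monotone-constrained fit takes no priority on direction when the Cox fit, or the planned unconstrained threshold or GAM fit, indicates risk increasing in the marker. In that case report both, state that monotonicity or no unmeasured confounding is in doubt, and present neither curve as established controlled VE.
- **Section 15.1:** describe monotonicity as assumed rather than known, and name the unconstrained fits already planned as the check on it. Those need 35 cases or fewer (Table 4), so they will be available whenever controlled VE, which needs 50, is run.
- **Section 16.2:** let an omnibus-test p-value count towards a CoP flag only if the estimated direction is protective.

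The cost is a few sentences and no new estimator. No interval or p-value is recomputed after a diagnostic, so the SAP's position in Section 12.3.3 against inference contingent on goodness-of-fit testing is respected. The downside is an inconclusive controlled VE result for markers that show this conflict.

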## 16.1 Synthesis Interpretation of Results

To structure the interpretation of the whole set of CoR and CoP results, we consider the Bradford-Hill criteria for supporting causality assessments:

- 1. Temporal sequence of association (vaccination causes generation of antibodies, which precede occurrence of the clinical disease outcome)
- 2. Strength of association (CoR magnitude)
- 3. Consistency of association (across studies and methods)
- 4. Biological gradient (may be interpreted as dose-response with greater Day 57 antibody corresponding to lower risk and greater VE)
- 5. Specificity (that the antibody marker is induced by vaccination not natural infection, and the antibody impacts the particular clinical endpoint being analyzed)
- 6. Plausibility [(supported by other COVID vaccines through study in efficacy trials and challenge (animal or human) trials, and by other potential studies such as natural history re-infection studies and monoclonal antibody prevention efficacy studies that could be challenge (animal or

human) or field trials])

- 7. Coherence (the causality assumption does not appear to conflict with current knowledge)
- 8. Experimental reversibility (if VE wanes to a low level then the antibody marker also wanes coincidently; if the Day 57 marker is a strong correlate for outcome during the period of high VE, then it becomes a weaker correlate against endpoints occurring during the later period of low VE; also could be supported if vaccine breakthrough cases tend to occur very early or late in follow-up when antibody levels are known to be relatively low)
- 9. Analogy (supported by other respiratory virus vaccines, and natural history studies or challenge studies of other respiratory virus vaccines)

We discuss evaluation of these criteria for Day 57 markers, where the same evaluations accounting for Day 29 markers are similarly relevant.

On temporal sequence, because the analyses are done in baseline negative individuals, generally the Day 57 antibody responses must be generated by the vaccine, and if the outcome occurs well after Day 57, then there is clear temporal ordering of vaccination causing antibodies followed by outcome. The nuance is outcome cases with event times near 7 days post Day 57, some of which could have been infected with SARS-CoV-2 prior to Day 57 and have relatively long incubation periods, possibly perturbing temporal ordering by creating naturally-induced rather than vaccine-induced antibody. However, the knowledge about the distribution of the time period between SARS-CoV-2 acquisition and symptomatic COVID, and the time needed for an infection to create an adaptive immune response, suggests that this issue could only haves a minor impact, and overall the temporal sequence criterion readily holds. Yet, the correlates analysis that stringently only includes cases with documented antigen negativity at both Day 29 and Day 57 may be helpful for evaluating the temporal sequence criterion.

On strength of association, this is directly quantified in all of the analyses as a core output of each method, quantified by point estimates and confidence in-

terval estimates of covariate-adjusted association parameters or causal effect parameters.

On consistency of association, checking for similar estimates and inferences across the multiple vaccine efficacy trials will be relevant. The fact that all of the tested vaccines are designed to protect through induction of antibody to Spike protein suggest that consistency is plausible. The vaccine platform needs to be accounted for in this evaluation, where consistency may be expected for vaccines of a given type (e.g., mRNA vaccines, Spike protein vaccines, viral vector vaccines with a similar vector), whereas across types a consistent body of evidence would be very helpful, but not a requirement. FDA guidance has stipulated that a surrogate endpoint for one vaccine platform is not necessarily expected to hold for another, and that evidence for one platform would not be seen on its own as support for a surrogate endpoint for another.

In addition, we will plan to study predictiveness of the estimated optimal surrogate built on each single trial data set applied to the other trial data sets, quantified by AUC on new data sets. Moreover, consistency of association may be assessed in another sense - by studying whether the different CoR methods tend to reveal a consistent directionality and pattern of an antibody marker correlated with risk, and whether the different CoP methods tend to reveal a consistent directionality and pattern of an antibody marker connected to vaccine efficacy (as measured by the various causal effect parameters) and with different versions of vaccine efficacy. A common core element of all of the CoR and CoP methods is covariate-adjusted estimation of marker-conditional risk in vaccine recipients, e.g. of marginal conditional risk  $E_X[P(T \le t_F | S = s, A = 1, X)]$  or  $E_X[P(T \le t_F | S \ge s, A = 1, X)].$ Generally, if an estimate of this function shows strongly decreasing risk with s, then likely all of the CoR analyses will detect such a decrease, and the CoP analyses will detect a version of vaccine efficacy increasing in s. A nuance in looking for consistency of results across methods stems from the fact that different methods have different power to detect the same effect; because of this fact, consistency in magnitude (point estimate) and directionality are more important than consistency in inference/statistical significance.

The fact that all of the methods adjust for the same set of baseline covariates X will aid the ability to compare the results across methods in an interpretable manner. This discussion highlights the relevance of adjusting for the same set of baseline covariates across the different efficacy trials, although our choice to do covariate-adjustment through marginalization (rather than through conditional association parameters) lends some resilience to this issue.

Our comments on consistency of association have supposed a given study endpoint, such as COVID. Another dimension of consistency evaluation could include comparing results across endpoints. On the one hand, consistency in evidence across endpoints could strengthen the case for a CoP, especially for endpoints in the same 'class' such as moderate disease and severe disease. On the other hand, the greater the difference between endpoints, the less relevant consistency may be, because the vaccine may protect through different mechanisms against each endpoint (one potential example is prevention of asymptomatic infection vs. prevention of severe disease). Thus evidence for a CoP for a given endpoint should not necessarily be down-graded based on evidence that the same marker does not appear to be a CoP for another endpoint.

On biological gradient, many of the methods are flexible and designed to detect a dose-response pattern of antibody with risk or antibody with vaccine efficacy, with tabular and graphical output of point and confidence interval estimates designed to reveal dose-response.

On specificity, as noted above antibodies generally are almost surely vaccineinduced given the analysis is done in baseline negative individuals, although with nuance that care is needed to evaluate whether some vaccine breakthrough cases may have had SARS-CoV-2 acquisition unusually early in follow-up (e.g., prior to second vaccination). In addition, the assays are validated for measuring specific anti-SARS-CoV-2 antigen response. Moreover, the Day 57 antibody markers can be verified to be negative in all or almost all baseline negative placebo recipients. Therefore, the specificity criterion should readily hold, with the proviso of the complication of the possible inclusion of unusually early infections as vaccine breakthrough cases in some analyses.

On coherence, the results will be interpreted in the light of knowledge of immune correlates of protection for the same vaccine in animal challenge studies (and human challenge studies as available), where multiple studies have demonstrated that both binding and neutralizing antibodies are a correlate of protection.

The results will also be interpreted in light of any knowledge available on passively administered SARS-CoV-2 monoclonal antibodies for prevention of SARS-CoV-2 infection or COVID disease, either in challenge studies (animals or humans) or efficacy trials. In addition, the results will be interpreted in light of results on the antibody markers as correlates of re-infection in natural history studies. Note we are cautious to not use correlates studies in alreadyinfected individuals, because the fact of infection may readily change the nature of a correlate of protection.

On experimental reversibility, we will evaluate whether the strength of association of the Day 57 CoRs and CoPs weakens when restricting to outcomes occurring more distal to vaccination. If the vaccine efficacy is found to wane over time, and the antibody marker wanes over time, then this decrease in the strength of association would be consistent with antibody as a correlate of protection. In contrast, if vaccine efficacy and antibody waned over time, but the strength of a Day 57 CoR and CoP was the same regardless of the timing of outcomes, it might call into question the role of the antibody marker as a CoP. The Stage 2 correlates analyses will also be helpful, where experimental reversibility could be supported simply by coincident waning of VE and waning antibody.

Experimental reversibility may also be supported by "population-level" correlates analyses, a term sometimes used in reference to meta-analysis that associates the level of VE with the population-level of a Day 57 marker across subgroups or trials; e.g. the population-level Day 57 marker response may be summarized by the geometric mean titer or geometric mean concentration.

On analogy, perhaps the most relevant vaccines to consider are vaccines

against other respiratory viruses, including influenza vaccine and RSV vaccines. The fact that neutralizing antibodies are a CoR and CoP for both inactivated and live virus vaccines supports that neutralizing antibodies can be a CoP for SARS-CoV-2. In addition, there is ongoing correlates of protection analysis of Novavax's Phase 3 RSV vaccine efficacy trial, that is evaluating binding antibody and neutralizing antibody CoRs and CoP correlates for severe respiratory disease in infants of vaccinated pregnant mothers (submitted). Once those results are available, they will aid in checking the analogy (and coherence) criterion.

The univariate CoR analyses essentially assess five Day 57 antibody biomarkers. The questions arise as to how do we select which biomarker seems to be the best-supported CoP, and do we need to be concerned about multiplicity adjustment issues? Given the multifactorial nature of the assessment involving biology and statistics, we for the most part avoid an approach that tries to pre-specify a quantitative ranking system; rather our approach presents the results of each marker side by side and allows human synthesis and interpretation. To guard against errors in this subjective process, we suggest that consistent results across analyses of a given trial, and consistent results (and predictive validation) across multiple trials, will provide particularly strong guidance for interpreting results. For example, if a particular Day 57 antibody marker shows remarkably consistent results in being a strong CoR and supported CoP but the other readouts do not, it may emerge as the best-supported CoP. In addition, the superlearning CoR estimated optimal surrogate objective has a special place of importance, because it includes variable importance quantification, providing some quantitative guidance on ranking the predictivneness of markers. This variable importance will be defined both internal to a given trial and based on external validation on the other efficacy trials. The metrics of CV-AUC and AUC on new trials quantifies evidence for signal in the data in a way that is protected from risk of false positive results, by virtue of having two layers of cross-validation used to estimate CV-AUC and hence avoid over-fitting. In addition, the CoR analvses use multiple hypothesis testing adjustment to help ensure clear signals and not false positive results (see Section 12.4.2). We also need a plan for

minimizing the risk of false positive results for CoP analyses, which we now address.

